15.4.2 Analysis of secondary endpoints

The 4 secondary efficacy endpoints evaluate the impact of 16 weeks of treatment on (I) change in SLR, (II) change in the average of maximum TBR values (MeanTBR_{max}) of each aortic subsegment (ascending, aortic arch, descending, suprarenal, and infrarenal aorta), (III) association between change in PASI and change in aortic wall FDG-uptake, (IV) association between change in PASI and change in SLR.

These endpoints will be evaluated by testing the hypothesis of no difference between brodalumab and placebo. The endpoints will be analysed and presented for the per protocol analysis set.

The change from baseline to Week 16 in SLR and aortic subsegment FDG-uptake are continuous endpoints and will be analysed using a repeated measurements model.

If applicable, a supportive multivariate analysis will be performed as described in section 12.4.1.

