8.5 Trial rationale and hypothesis

We hypothesize that aortic wall inflammation is increased in subjects with moderate-to-severe psoriasis and that this inflammatory process may be reduced by effectively treating psoriasis by brodalumab. Furthermore, we hypothesize that systemic inflammation, as indicated by increased splenic FDG uptake, may be reduced by brodalumab therapy, and that this reduction may be associated with reduced aortic wall inflammation. The rationale for the duration of follow-up is based on previous clinical trials showing a rapid and effective response to brodalumab on signs and symptoms of psoriasis.

Trial ID (EudraCT No.): 2017-003697-14	Date: 23.02.2018	Page Version 2.3
---	------------------	---------------------

The purpose of the study is to assess the effect of IL-17RA blockade by brodalumab on aortic wall inflammation and splenic inflammation in patients with moderate-to-severe psoriasis.

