9.1 Trial objectives and endpoints

Objectives	Endpoints
Primary objective To assess the change in aortic wall inflammation from baseline to week 16 in brodalumab treated psoriasis subjects compared to placebo.	Primary endpoint 
 Change in the average of maximum TBR values (MeanTBR_{max}) of the entire aorta from baseline to week 16
Secondary objectives To assess the change in splenic inflammation from baseline to week 16 in brodalumab treated psoriasis subjects compared to placebo. To assess the change in aortic wall subsegment inflammation from baseline to week 16 in brodalumab treated psoriasis subjects compared to placebo. To assess whether changes in skin inflammation is associated with changes in aortic wall inflammation and/or changes in splenic inflammation.	Secondary endpoint 
 Change in the spleen-to-liver ratio (SLR) based on splenic and liver mean standardised uptake values (SUV_{mean}) Change in the average of maximum TBR values (MeanTBR_{max}) of the ascending, aortic arch, descending, suprarenal, and infrarenal aorta from baseline to week 16 Association between change in PASI and change in aortic wall MeanTBR_{max} Association between change in PASI and change in SLR
Additional secondary objectives To assess the change in subcutaneous adipose tissue inflammation from baseline to week 16 in	
 Change in the average of maximum SUV values (MeanSUV_{max}) of the abdominal

Trial ID (EudraCT No.): 2017-003697-14	Date: 23.02.2018	Page Version 2.3
---	------------------	---------------------

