15.4.3 Analysis of other endpoints

Change in acute phase proteins at week 16 between groups and change in abdominal subcutaneous adipose tissue FDG-uptake will be analysed using a repeated measures model. Changes in cytokine expression and gene expression in optional skin samples will be analysed using a repeated measures model. Association between change in PASI and change in subcutaneous adipose tissue as well as the association between change in TBR/SLR and psoriasis-specific genotypes will be computed using applicable correlation coefficients.

Trial ID (EudraCT No.): 2017-003697-14	Date: 23.02.2018	Page Version 2.3
---	------------------	---------------------

16

REFERENCES

2. Christophers E. Psoriasis – epidemiology and clinical spectrum. *Clinical and Experimental Dermatology*. 2001;26(4):314-320.
3. Bowcock AM. The genetics of psoriasis and autoimmunity. *Annu Rev Genomics Hum Genet*. 2005;6:93-122.

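### Section 15.4.2 sets a between-arm null for all four secondary endpoints, but endpoints III and IV are associations whose objective asks only whether an association exists

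*Protocol*

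**What the plan says.** Protocol section 15.4.2 opens with "The 4 secondary efficacy endpoints evaluate the impact of 16 weeks of treatment on (I) change in SLR", goes on to the aortic subsegments as II, and completes the list with "III) association between change in PASI and change in aortic wall FDG-uptake, (IV) association between change in PASI and change in SLR". The hypothesis follows: "These endpoints will be evaluated by testing the hypothesis of no difference between brodalumab and placebo". No endpoint is exempted.

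The only model named in 15.4.2 is for I and II: the change "in SLR and aortic subsegment FDG-uptake are continuous endpoints and will be analysed using a repeated measurements model".

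The objectives in section 9.1 are of two kinds. The one behind endpoint I is "To assess the change in splenic inflammation from baseline to week 16 in brodalumab treated psoriasis subjects compared to placebo", and the subsegment objective behind II likewise names placebo. The one behind III and IV is "To assess whether changes in skin inflammation is associated with changes in aortic wall inflammation and/or changes in splenic inflammation", with no comparator.

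Section 15.4.3 treats other associations differently. It assigns correlation coefficients to the PASI–adipose association and to the genotypes: "the association between change in TBR/SLR and psoriasis-specific genotypes will be computed using applicable correlation coefficients". It sets no between-arm null for these and does not mention III or IV.

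**The concern.** The objective behind III and IV calls for a null of no association. The null that 15.4.2 states can apply to an association only as equality of that association between the arms. These are different hypotheses, and neither implies the other. If PASI change and aortic change went together equally in both arms, the objective would be met and the stated null would be true. A rejection would show that the arms differ, not that skin and vessel (or spleen) change together.

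This is not detail left to a statistical analysis plan. The protocol states a hypothesis that does not fit its own objective. A later plan that follows the sentence inherits the mismatch, and one that corrects it departs from the protocol. Two analysts could each report a different test as the prespecified one.

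**Working it through.** **Inputs.** From section 15.1: 22 evaluable per arm, alpha 0.05, means 2.4 and 2.1, SD 0.35. From 10.2: 25 randomised per arm. From 15.4.1: a two-sided test (stated for the primary endpoint). The protocol gives no correlation between PASI change and TBR or SLR change, so every r below is an assumption.

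**The plan's own figure.** n per arm = 2(1.960 + 0.842)² × 0.35² / 0.3² = 21.4, so 22. Power at 22 per arm is 81.1% by the normal approximation and 79.3% by the noncentral t. The stated 22 per arm and 80% reproduce. They concern the primary endpoint only.

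**The two tests by Fisher's z, 22 per arm.**
- Equality of the two correlations: SE = √(1/19 + 1/19) = √(2/19) = 0.324.
- A common within-arm correlation equal to zero: SE = √(1/38) = 0.162.
- Same r in both arms: the expected difference in z is 0, so the first test rejects at about alpha by construction. The second has power Φ(atanh(r)/0.162 − 1.96), which is 48% at r = 0.3, 74% at 0.4, 92% at 0.5 and 99% at 0.6.
- Correlation needed for 80% power: tanh(2.802 × 0.324) = 0.72 in one arm against 0 in the other for the first test; tanh(2.802 × 0.162) = 0.43 in both arms for the second.

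**Simulation.** Bivariate normal changes, 22 per arm, 40,000 trials per setting. The between-arm test was run as an arm-by-PASI-change interaction and as a Fisher z comparison. The association test was the arm-adjusted slope.

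| Assumed setting | Interaction | Fisher z comparison | Arm-adjusted association |
|---|---|---|---|
| r = 0.2 in both arms | 5.0% | 5.2% | 25.3% |
| r = 0.3 in both arms | 4.8% | 4.9% | 50.5% |
| r = 0.5 in both arms | 5.0% | 4.9% | 93.8% |
| r = 0.5 versus 0.2 | 16.8% | 18.8% | 64.8% |
| r = 0.5 versus 0, equal spread | 37.9% | 41.0% | 37.8% |
| r = 0.3 versus 0, equal spread | 16.0% | 16.5% | 16.3% |

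**Unequal spread of PASI change.** With the same r in both arms and an SD ratio of 2 to 3, the slopes differ although the correlations do not. At r = 0.2, 0.3 and 0.5 the interaction rejects 7–9%, 9–14% and 21–37%. The Fisher z comparison stays at about 5%, and the arm-adjusted slope rejects 21–23%, 42–47% and 88–91%.

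With r = 0.5 in one arm only and an SD ratio of 2 to 3, the order depends on which arm carries the association:
- Narrower-spread arm: interaction 55–60%, arm-adjusted 19–12%.
- Wider-spread arm: interaction 19–13%, arm-adjusted 55–60%.

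**Overall against arm-adjusted.** Assume no within-arm association, arms 2 to 3 SD apart in PASI change, a TBR difference of 0.3 and an SD of TBR change of 0.35 (the protocol's 0.35 is cross-sectional; using it for change assumes a visit-to-visit correlation of 0.5). The standardised TBR difference is 0.3/0.35 = 0.857. Across both arms:
- 2 SD: r = (2 × 0.857/4) / √[(1 + 4/4)(1 + 0.857²/4)] = 0.43/√(2.0 × 1.18) = 0.28.
- 3 SD: r = (3 × 0.857/4) / √[(1 + 9/4)(1 + 0.857²/4)] = 0.64/√(3.25 × 1.18) = 0.33.

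The unadjusted correlation is then significant in 47–62% of trials, and the arm-adjusted test (run at 2 SD) in about 5%. The two estimates answer different questions, so the plan has to say which is primary.

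**The case against.** The strongest reply is that the sentence is a general lead-in meant for I and II. Only those two get a model, no comparison of correlations between arms is described anywhere, 9.1 defines III and IV as associations, and 15.4.3 uses correlation coefficients for the sister PASI–adipose association. This is probably what was intended. It does not remove the mismatch, because the sentence covers all four endpoints and 15.4.3 does not extend its method to III and IV.

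A second reply is that the by-arm reading is coherent. The lead-in presents all four endpoints as effects of treatment, and whether treatment alters the skin–vessel association is a fair question. It is not the question in 9.1.

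A third reply is that the 5% figure follows from the definition of the test and that the between-arm test is not uniformly weaker. Both statements are correct: the tests tie when the association is in one arm with equal spread, and the interaction is stronger when that arm has the narrower spread. A reader might infer that the literal rule always costs power; the figures do not support that. What stands is that the rule answers a different question.

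A reader might also infer that an unadjusted correlation would be spurious and that arm adjustment is required. The documents do not support this either. Section 9.1 does not condition on arm, and section 8.5 hypothesises that "this inflammatory process may be reduced by effectively treating psoriasis by brodalumab", so covariation driven by treatment may be part of the question. The 47–62% above reflects a true overall correlation of about 0.28 to 0.33, not false positives.

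**Conclusion.** The concern holds as a mismatch between the stated null and the objective for two of the four secondary endpoints. Followed literally, 15.4.2 would not test the objective behind III and IV. The roughly 5% rejection rate under an equal association applies when correlations are compared, or to an interaction test with equal PASI-change spread. Every power figure rests on an assumed r, normal changes and 22 per arm, and the protocol gives no planning figure for SLR.

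The severity is minor. The primary endpoint, endpoints I and II, the sample size and data collection are untouched, the sentence was probably not meant for III and IV, and the protocol attaches no success criterion to them. At r = 0.2 to 0.3 the arm-adjusted test of association has only 25–50% power at this sample size.

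**What to change.** In section 15.4.2, limit the between-arm null to endpoints I and II. For III and IV, state that the null is no association between PASI change and change in MeanTBRmax (or SLR), meaning a correlation or slope of zero, and that the estimate will be reported with a 95% CI.

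Before unblinding, name which estimate is primary, the overall (unadjusted) or the arm-adjusted one, and report both together with by-arm estimates. The overall estimate includes treatment-driven covariation; the arm-adjusted one shows the association within arms. Arm adjustment is an option here, not a required correction.

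The cost is a few sentences and a little extra analysis, with no new data.

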15.4.3 Analysis of other endpoints

Change in acute phase proteins at week 16 between groups and change in abdominal subcutaneous adipose tissue FDG-uptake will be analysed using a repeated measures model. Changes in cytokine expression and gene expression in optional skin samples will be analysed using a repeated measures model. Association between change in PASI and change in subcutaneous adipose tissue as well as the association between change in TBR/SLR and psoriasis-specific genotypes will be computed using applicable correlation coefficients.

Trial ID (EudraCT No.): 2017-003697-14	Date: 23.02.2018	Page Version 2.3
---	------------------	---------------------

16

REFERENCES

2. Christophers E. Psoriasis – epidemiology and clinical spectrum. *Clinical and Experimental Dermatology*. 2001;26(4):314-320.
3. Bowcock AM. The genetics of psoriasis and autoimmunity. *Annu Rev Genomics Hum Genet*. 2005;6:93-122.

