8.4 Experience with experimental medicinal product

Brodalumab is a recombinant fully human monoclonal immunoglobulin IgG2 antibody that binds with high affinity to human IL-17RA and blocks the biological activities of the pro inflammatory cytokines IL-17A, IL-17F, IL-17A/F heterodimer and IL-17C and IL-17E (IL-25).

Trial ID (EudraCT No.): 2017-003697-14	Date: 23.02.2018	Page Version 2.3
---	------------------	---------------------

Brodalumab is approved for the treatment of moderate to severe plaque psoriasis in adult patients who are candidates for systemic therapy. The trade name of brodalumab in Europe is Kyntheum and it is marketed by LEO Pharma A/S. Kyntheum is available as a 210 mg solution for injection.

The approval of brodalumab is based on the results of three multicenter, randomized, double-blind, controlled trials (AMAGINE 1, 2, and 3) that enrolled a total of 4373 subjects 18 years of age and older with at least a 6-month history of moderate to severe plaque psoriasis, defined as having a minimum affected body surface area (BSA) of 10%, a Psoriasis Area and Severity Index (PASI) score ≥ 12 , a static Physician's Global Assessment (sPGA) score ≥ 3 in the overall assessment (plaque thickness/induration, erythema, and scaling) of psoriasis on a severity scale of 0 to 5, and who were candidates for systemic therapy or phototherapy. In all three trials, subjects were randomized to subcutaneous treatment with placebo or brodalumab 210 mg at Weeks 0, 1, and 2, followed by treatments every 2 weeks through Week 12. In the two active comparator trials (AMAGINE 2 and 3), subjects randomized to ustekinumab received a 45 mg dose if their weight was less than or equal to 100 kg and a 90 mg dose if their weight was greater than 100 kg at Weeks 0, 4, and 16, followed by the same dose every 12 weeks. At week 12, the proportion of patients attaining a 75% improvement from the baseline Psoriasis Area and Severity Index (PASI 75) was similar among the three phase III trials (AMAGINE-1, 83%; AMAGINE-2, 86%; AMAGINE-3, 85%). Brodalumab remained efficacious through 52 weeks of treatment.⁴⁶

Most common adverse reactions (incidence $\geq 1\%$) were arthralgia, headache, fatigue, diarrhea, oropharyngeal pain, nausea, myalgia, injection site reactions, influenza, neutropenia, and tinea infections.

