
brodalumab treated psoriasis subjects compared to placebo and whether this change is associated with changes in skin inflammation.
 
To assess the change in soluble inflammatory biomarkers from baseline to week 16 in brodalumab treated psoriasis subjects compared to placebo.
 
To assess whether the change in aortic wall inflammation and/or splenic inflammation is associated with psoriasis-specific genotypes.
 
To assess the change in gene expression and cytokine expression in paired lesional and non-lesional psoriatic skin from baseline to week 16 in brodalumab treated psoriasis subjects compared to placebo.
	
 subcutaneous adipose tissue from baseline to week 16 Association between change in PASI and change in subcutaneous adipose tissue MeanSUV_{max}. Changes in acute phase proteins from baseline to week 16 Correlation between changes in both aortic meanTBR_{max} and SLR and presence of HLA-B*08, HLA-C*06:02, HLA-B*27, HLA-B*38 and HLA-B*39 Changes in gene expression and cytokine expression in skin samples from baseline to week 16 Correlation with changes in mean aortic TBR_{max} and SLR.
---	---

10 Trial design

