10.2 Number of subjects needed

Assuming a screening failure rate of 20%, approximately 62 patients will be screened and 50 patients will be included and randomly assigned to either brodalumab or placebo (1:1; 25 patients in each arm).

The statistical power calculation (section 14.1) includes the risk of drop-out before completion of the second FDG-PET/CT.

Trial ID (EudraCT No.): 2017-003697-14	Date: 23.02.2018	Page Version 2.3
---	------------------	---------------------

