15.1 Sample size

Derived from our investigations of vascular inflammation in psoriasis patients and control subjects, we expect a mean aortic TBR_{max} of 2.4 with a standard deviation of 0.35 in the psoriasis subjects. After successful treatment with biologic agents, we expect the MeanTBR_{max} in the psoriasis subjects to be reduced to 2.1 with SD 0.35. Based on these assumptions and an alpha-level of 0.05 we calculate that 22 psoriasis subjects in each study arm will provide a power of 80% to detect a difference between the groups. By choosing a sample size of 25 psoriasis subjects we allow for a dropout of 3 subjects at follow-up without reducing power significantly.

Trial ID (EudraCT No.): 2017-003697-14	Date: 23.02.2018	Page Version 2.3
---	------------------	---------------------

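### Section 15.4.3 gives only a correlation coefficient for change in PASI against change in fat uptake, with no treatment-arm term; pooled over arms, it would mix two parallel drug effects with any within-patient link

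*Protocol*

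**What the plan says.** Section 9.1 lists, among the additional secondary objectives, the change in subcutaneous adipose tissue inflammation under brodalumab compared with placebo, and "whether this change is associated with changes in skin inflammation". The matching endpoint begins "Association between change in PASI and change in subcutaneous adipose tissue", with fat uptake measured as MeanSUVmax.

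Section 15.4.3 gives the method. One sentence covers "Association between change in PASI and change in subcutaneous adipose tissue as well as the association between change in TBR/SLR and psoriasis-specific genotypes", and both "will be computed using applicable correlation coefficients". It does not say whether the coefficient is pooled over arms, computed within arm, or partial. The between-group comparison of fat uptake is handled separately in the same section by a repeated measures model.

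The allocation in section 10.2 is "1:1; 25 patients in each arm". Section 8.4 gives week-12 PASI 75 response rates for brodalumab, in per cent, as "AMAGINE-1, 83%; AMAGINE-2, 86%; AMAGINE-3, 85".

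The associations of PASI change with aortic uptake and with SLR are in section 15.4.2. No correlation method is named there; the only statement is "These endpoints will be evaluated by testing the hypothesis of no difference between brodalumab and placebo".

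**The concern.** In a randomised comparison with a highly effective drug, change in PASI largely tells you which arm a subject was in. If the drug also lowers FDG uptake in fat, by any route, the subjects with large skin improvement will tend to be those with lower fat uptake simply because both groups are the brodalumab arm. A coefficient over all subjects then restates the two treatment effects.

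The section 9.1 question goes further than that. The treatment effect on fat is already reported by its own model, so the association adds information only if it shows whether subjects whose skin improves more also improve more in fat. A pooled coefficient cannot separate such a link from two parallel drug effects. The stake is the interpretation of one additional secondary endpoint.

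**Working it through.** **The plan's own figure.** The only sample size in the protocol is for the primary aortic endpoint (section 15.1): means 2.4 and 2.1, SD 0.35, "an alpha-level of 0.05", two-sided as in section 15.4.1, power 80%.

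n per arm = 2 × (1.96 + 0.842)² × 0.35² / 0.30² = 2 × 7.85 × 0.1225 / 0.09 = 21.4, rounded up to 22.

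This agrees with the stated 22. The protocol gives no figure for the correlation analyses, so 22 evaluable subjects per arm is carried forward.

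**Inputs that must be assumed.** Let d1 be the between-arm difference in PASI change and d2 the between-arm difference in change in fat uptake, each in within-arm SD units.

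- d1: section 8.4 supports a large skin effect, but the protocol gives neither a placebo rate nor an SD of PASI change. Range taken: 1 to 3.
- d2: the protocol gives no treatment effect on fat. Range taken: 0 to 0.857. The upper value is 0.30/0.35 from the aortic planning assumptions; it is borrowed, and its SD is that of TBR values, not of changes.

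**Formula.** With 1:1 allocation and zero correlation within each arm, the between-arm covariance is 0.25 × d1 × d2, and each variance becomes 1 + 0.25 × d². So

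pooled r = 0.25 d1 d2 / √[(1 + 0.25 d1²)(1 + 0.25 d2²)].

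For d1 = 2:

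- d2 = 0.3: 0.15 / √(2 × 1.0225) = 0.105
- d2 = 0.5: 0.25 / √(2 × 1.0625) = 0.171
- d2 = 0.857: 0.4285 / √(2 × 1.1836) = 0.279

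**How often a 5% two-sided test of r = 0 would reject.** Simulation used 20,000 trials per setting, 22 per arm, and no true within-arm link:

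| d1 | d2 | expected pooled r | rejection, arms pooled | rejection, arm removed |
|---|---|---|---|---|
| 1 | 0.3 | 0.07 | 7.3% | 5.0% |
| 1 | 0.5 | 0.11 | 10.9% | 4.9% |
| 1 | 0.857 | 0.18 | 21.5% | 5.2% |
| 2 | 0 | 0.00 | 4.9% | 5.2% |
| 2 | 0.3 | 0.11 | 10.4% | 5.0% |
| 2 | 0.5 | 0.17 | 19.8% | 5.0% |
| 2 | 0.857 | 0.28 | 47.0% | 5.0% |
| 3 | 0.3 | 0.12 | 12.5% | 5.1% |
| 3 | 0.5 | 0.20 | 26.7% | 5.2% |
| 3 | 0.857 | 0.33 | 61.9% | 4.9% |

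Hand check with Fisher's z for d1 = 2, d2 = 0.5: atanh(0.171) × √(44 − 3) = 0.173 × 6.40 = 1.11. The chance of exceeding 1.96 is P(Z > 0.85), about 20%, which agrees with the simulation.

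With all 25 per arm evaluable, the d2 = 0.857 rows rise to 52.4% (d1 = 2) and 67.5% (d1 = 3). Removing the arm means brings the mean correlation to 0.00 in every setting.

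**The case against.** The strongest reply is that pooling is inferred from silence. A partial or within-arm coefficient is also a correlation coefficient that could apply, and an analysis plan that is not shown may settle this. That is fair as far as it goes: a reader might infer that the protocol prescribes an unadjusted coefficient, and it does not. But the section does state a method, and its wording most naturally selects a type of coefficient, not an adjustment. Following the sentence literally yields a pooled value.

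Second, section 9.1 asks only whether the changes are associated, and an overall association is a legitimate description. This stands as a limit on the point: the pooled value is not meaningless, but it cannot by itself be read as a skin-fat link.

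Third, section 15.4.3 states no hypothesis test for this association. The rejection rates therefore show how large the artefact could be; they are not the error rate of a planned test.

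Fourth, 0.857 SD belongs to the aorta. Section 8.3 does report a patient-control gap in fat TBRmax of 0.49 (SD 0.18) versus 0.31 (SD 0.12). That is 0.18 / √[(0.18² + 0.12²)/2] = 0.18 / 0.153 = 1.18 SD, so 0.857 is not extreme. But it is a cross-sectional gap on a different measure, not a treatment effect.

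Two wider readings are tempting and fail. A reader might extend the argument to the genotype correlations in the same sentence. HLA type precedes randomisation and is independent of arm in expectation, so a pooled coefficient is not biased. In simulations with no genotype effect, drug effects of 0.5 or 0.857 SD and assumed carrier frequencies of 10% to 50%, the unadjusted test rejected in 4.7% to 5.2%. An arm term there only reduces noise. A reader might also infer that the PASI-aorta and PASI-SLR associations share the fault, but section 15.4.2 names no correlation method for them.

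**Conclusion.** The point holds for one analysis: change in PASI against change in subcutaneous adipose uptake. As worded, section 15.4.3 leads naturally to a coefficient confounded by treatment arm, which cannot answer whether the two changes go together within patients.

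The size is conditional on three things: pooling of the arms, a large arm separation in PASI change, and a real drug effect on fat uptake. At a 2 SD skin separation and 22 per arm, the spurious r runs from about 0.11 to 0.28, and a 5% test would reject in about 10% to 47% of trials, as the assumed fat effect goes from 0.3 to 0.857 SD. If brodalumab does not change fat uptake, there is no artefact. It does not follow that a false positive is likely, because the documents supply no fat effect. The primary endpoint and the sample size are untouched.

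**What to change.** State in section 15.4.3 that the association between change in PASI and change in adipose uptake is estimated by regressing the change in uptake on the change in PASI with treatment arm as a covariate. Report the arm-adjusted slope and the partial correlation, each with a 95% CI, and show the association separately by arm. A pooled coefficient may still be given if it is labelled as descriptive.

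For consistency, use the same arm term if the PASI-aorta and PASI-SLR associations in section 15.4.2 are analysed as correlations. No change is needed for the genotype correlations.

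The cost is a sentence or two of protocol text, one degree of freedom, and a possibly smaller association than the pooled one.
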